6.2 Treatment Delays

The study medications may be held for toxicity for up to four weeks before the participant must be removed from the study. Exceptions to this requirement are possible should the principal investigator agree that the patient may continue despite the length of time off drug.

Study medications may be held independently of each other if toxicity is felt by the treating investigator to be attributed to one or two of the three medications (e.g., a patient may continue to receive their LY3022855 on schedule while holding their vemurafenib and/or cobimetinib).

If the study medication(s) is/are placed on hold for toxicity, the counting of cycle days and assessment schedule will continue without interruption. For example, a patient who does not receive their cycle 2 day 15 infusion of LY3022855 due to toxicity will proceed with their next scheduled infusion and visit (cycle 2 day 22). Additional interim visits will be conducted as clinically necessary to manage toxicity. The cycle will not restart for dosing delays due to toxicity. Exceptions to this are possible for significant treatment delays (\geq 2 weeks) after a discussion with the principal investigator. If an exception is made to restart the cycle for a participant in the phase II portion of the trial, tumor evaluations should continue as previously scheduled (tumor evaluations should not be delayed).

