5.4 Definition of Dose-Limiting Toxicity (DLT)

Dose-limiting toxicity is based on version 4.03 of the NCI Common Terminology Criteria for Adverse Events (CTCAE). DLT refers to toxicities experienced during the first cycle of treatment that are possibly, probably, or definitely related to the study medication regimen. A DLT will be defined as follows:

- \geq Grade 3 non-hematological toxicity. Exceptions will be made for:
 - Nausea, vomiting, diarrhea, or constipation that can be controlled with appropriate care. Grade 3 and grade 4 nausea, vomiting, diarrhea, or constipation should be considered a DLT if persisting more than 48 hours despite maximum supportive intervention.
 - Grade 3 rash or photosensitivity lasting fewer than 8 days, or that can be controlled with appropriate care. Grade 3 rash or photosensitivity should be considered a DLT if it persists for more than 8 days and cannot be managed despite maximum supportive

intervention.

- Grade 3 thrombocytopenia with clinically significant bleeding
- Grade 4 thrombocytopenia
- \geq Grade 3 febrile neutropenia
- Grade 4 anemia
- Holding of any study medication due to toxicity for a period of greater than 8 consecutive days or two separate periods of any duration during the first cycle.
- Any other significant toxicity deemed by the principal investigator to be dose limiting (for example, any toxicity that is at least possibly related to the study medication regimen that results in the withdrawal of the patient from the study during cycle 1).

Management and dose modifications associated with the above adverse events are outlined in **6.1**, **6.2**, and **6.3**.

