5.6 Criteria for Taking a Participant Off Protocol Therapy

Duration of therapy will depend on individual response, evidence of disease progression and tolerance. In the absence of treatment delays due to adverse event(s), treatment may continue indefinitely or until one of the following criteria applies:

- Disease progression, unless the patient is deriving clinical benefit as agreed upon with the principal investigator
- Intercurrent illness that prevents further administration of treatment
- Unacceptable adverse event(s) including those described in **5.4** and **6.1**
- Participant demonstrates an inability or unwillingness to comply with the oral medication regimen and/or documentation requirements

- Participant decides to withdraw from the protocol therapy
- General or specific changes in the participant's condition render the participant unacceptable for further treatment in the judgment of the treating investigator

Participants will be removed from the protocol therapy when any of these criteria apply. The reason for removal from protocol therapy, and the date the participant was removed, must be documented in the case report form (CRF). Alternative care options will be discussed with the participant.

For Centralized Subject Registrations, the research team submits a completed Off Treatment form to ODQ when a participant comes off study. This form can be found on the ODQ website or obtained from the ODQ registration staff.

For Decentralized Subject Registrations, the research team updates the relevant Off Treatment information in OnCore.

In the event of unusual or life-threatening complications, treating investigators must immediately notify the Overall PI, [name] at DFCI pager number [name].

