5.7 Duration of Follow Up

Participants will be followed until death after removal from protocol therapy. This follow up will be performed by review of the medical record, contact with care providers, and/or telephone contact as needed every 3-4 months.

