5.8 Criteria for Taking a Participant Off Study

Participants will be removed from study when any of the following criteria apply:

- Lost to follow-up
- Withdrawal of consent for data submission
- Death

The reason for taking a participant off study, and the date the participant was removed, must be documented in the case report form (CRF).

For Centralized Subject Registrations, the research team submits a completed Off Study form to ODQ when a participant comes off study. This form can be found on the ODQ website or obtained from the ODQ registration staff.

For Decentralized Subject Registrations, the research team updates the relevant Off Study information in OnCore.

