6.1 Specific Toxicity Management

Dose delays and modifications due to toxicity considered at least possibly related to LY3022855, vemurafenib, and/or cobimetinib will be made as indicated in the following tables. Please also see **6.2** and **6.3** for further guidance on allowed treatment delays and dose modifications:

Table 12: Management of Elevated AST/ALT

Table 12: Management of Elevated 119 1/1121		
AST (SGOT) and/or ALT (SGPT) Increase	Medication Management	
≤ Grade 2	No change.	
Grade 3, increase lasting less than 8 days	Hold study medications until resolution to ≤	
without evidence of other hepatic injury	grade 1 or baseline. Resume study medications	
	at the same dose level.	
Grade 3, increase lasting 8 or more days	Hold study medications until resolution to ≤	
without evidence of other hepatic injury	grade 1; resume study medications with one	
-OR-	dose level reduction.	
Grade 4, without evidence of other hepatic		
injury		
≥ Grade 3, with evidence of other hepatic	Discontinue protocol therapy.	
injury		

Liver transaminase elevations have been associated with all three study medications in previous clinical trials. Patients should be monitored for increases in their liver function tests and for other signs of possible hepatic injury as clinically appropriate and as indicated in the Study Calendar – **Table 23**.

Table 13: Management of Neutropenia

Table 15: Management of Neutropenia		
Neutrophil Count Decrease	Medication Management	
≤ Grade 2	No change.	
Grade 3, no associated fever or infection	Hold study medications until recovery to ≤	
-OR-	grade 2. Upon recovery, restart at the same	
Grade 4, decrease lasting less than 8	dose level.	
consecutive days		
≥ Grade 3, associated with a fever or	Hold study medications until recovery to ≤	
infection	grade 2. Upon recovery, resume with one dose	
-OR-	level reduction.	
Grade 4, decrease lasting 8 or more		
consecutive days		

Table 14: Management of Thrombocytopenia

Platelet Count Decrease	Medication Management
≤ Grade 2	No change.
Grade 3, no clinically significant bleeding	Hold study medications until recovery to ≤ grade 2. Upon recovery, restart at the same dose level.
Grade 3, associated with clinically significant bleeding -OR- Grade 4	Hold study medications until recovery to ≤ grade 2. Upon recovery, resume with one dose level reduction.

Table 15: Management of Rash or Photosensitivity

Tuble 10t Hamingement of Thompson 11th		
Rash or Photosensitivity	Medication Management	

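### Follow-up after protocol therapy collects survival only, so phase II patients who stop without progression have no planned progression data for the PFS endpoint after the off-treatment visit

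*Combined protocol and SAP*

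**What the plan says.** Several routes lead off therapy without progression. Section 5.6 lists unacceptable adverse events and opens with the condition "In the absence of treatment delays due to adverse event(s), treatment may continue indefinitely". Section 6.1 requires discontinuation for some toxicities and points to 6.2 and 6.3 "for further guidance on allowed treatment delays and dose modifications". Section 6.2 allows a toxicity hold of up to four weeks "before the participant must be removed from the study", unless the principal investigator agrees that "the patient may continue despite the length of time off drug".

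On what happens next, section 5.7 states: "Participants will be followed until death after removal from protocol therapy". This is done every 3-4 months by record review, contact with care providers or telephone, and 5.7 does not say what is collected. Study Calendar footnote K does: it confines this follow-up to survival status. Footnote O places the off-treatment evaluation within 30 days of the last LY3022855 dose.

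Section 13.1 makes PFS the primary phase II endpoint. Under 11.1.5, progression or death from any cause is an event, and a patient alive without progression is censored at the last disease evaluation. Section 13.1 censors at the date the patient was last known to be free of progression. When only survival is followed, that is the same date.

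**The concern.** A patient who stops for toxicity while still responding or stable drops out of progression follow-up. If that patient later progresses and is alive at the data cut, the progression is not seen and the record ends at the last scan. If the patient dies before the cut, the death counts as a PFS event on its own date.

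Two things follow. The trial loses events and event-free time in an analysis planned around only 12 events. The loss is also one-sided: among patients who stop early, those who die keep their full time and count as events, while those who live on lose all the event-free time after stopping. That pulls estimated PFS down and costs power when the combination works. Section 7.1 anticipates overlapping hepatotoxicity, CK elevation and cardiomyopathy, so stopping for toxicity is plausible in this trial.

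**Working it through.** **Inputs from 13.1.** 25 patients; uniform accrual over 12 months plus 12 months of follow-up; medians of 10 (null) and 20 months; one-sided 10% test (z = 1.2816); rejection if the observed median is at least 14.5 months; 12 events; 85% power.

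**Step 1: the plan's own figures.** With λ = ln 2/20 = 0.03466 and follow-up uniform on 12 to 24 months, expected events are 25 × [1 − (e^(−12λ) − e^(−24λ))/(12λ)] = 25 × [1 − (0.6598 − 0.4353)/0.4159] = 11.5, which rounds to the stated 12. For the Wald test on the log rate, power = Φ(√d × ln 2 − 1.2816), which is 85.8% at d = 11.5 and 86.9% at d = 12. The boundary is 10 × exp(1.2816/√12) = 14.48 months. All agree with the plan.

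**Step 2: the effect of following survival only.** The documents give no stopping rate and no post-progression survival, so these are assumed. Time to progression is exponential with the median under test. Post-progression survival is exponential with median 6 or 12 months. One or four of the 25 patients are assigned a stop time uniform on months 1-6 or 1-12, effective only if they are still progression-free (on average 0.65 to 0.89 of one patient, 2.6 to 3.5 of four). The hazard does not change after stopping. Each scenario has 200,000 simulated trials.

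Rule A scans every patient until progression. Rule B is footnote K: after stopping, a death is an event on its date and a living patient is censored at the stop. The Kaplan-Meier median is compared with 14.5 months.

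| True median | Rule, four stoppers | Post-progression median | Events | P(median ≥ 14.5) | Change |
|---|---|---|---|---|---|
| 20 | A | – | 11.51 | 86.1% | – |
| 20 | B, months 1-6 | 6 | 10.89 | 81.2% | −4.9 |
| 20 | B, months 1-6 | 12 | 10.62 | 82.3% | −3.8 |
| 20 | B, months 1-12 | 6 | – | 82.5% | −3.6 |
| 20 | B, months 1-12 | 12 | – | 83.2% | −2.9 |
| 10 | A | – | 17.62 | 9.1% | – |
| 10 | B, months 1-6 | 6 | 16.80 | 8.5% | −0.6 |
| 10 | B, months 1-6 | 12 | 16.39 | 9.3% | +0.2 |

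Rule A gives 9.1% and 86.1%, close to the planned 10% and 85%. With one stopper the loss at 20 months is 0.6 to 1.3 points. Across all scenarios the change at 10 months lies between −0.6 and +0.5 points.

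**Step 3: cross-checks.** With the Wald test in place of the median rule, power under rule A is about 90%. It falls to about 89% with one stopper and to about 85-87% with four, a loss of similar size. A simpler calculation treats stopping as exponential censoring and ignores later deaths. With 5%, 10%, 20% or 30% of patients censored this way by 12 months, expected events at 20 months are 11.1, 10.7, 9.9 and 9.1, and power is 84.8%, 83.8%, 81.7% and 79.2%, against 85.8% with none.

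**The case against.** The best defence is that other sections keep disease assessment going. Sections 11 and 11.1 call for re-evaluation every eight weeks and do not say that it ends with therapy. Section 13.2 plans up to a further year to observe response and survival in the last patient. Section 13.4.2 assesses all eligible patients for response despite major therapy deviations. Section 5.7 provides record review without limiting its content. None of these states that progression is followed after therapy stops, and footnote K, the only text that says what is collected then, excludes it. The note in 11.1.3.4 asks for progression to be documented after discontinuation, but for patients reported as having symptomatic deterioration.

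A reader might infer that there are no progression data at all once therapy stops. That goes too far. The calendar's radiology row is damaged in the text available and may show imaging at the off-treatment visit. The gap begins after that visit.

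A reader might also infer from 6.2 that a long toxicity hold takes the patient off study and ends survival follow-up. The documents do not support this. The exception in 6.2 concerns time off drug, and 6.3 uses protocol therapy for the parallel dose-reduction rule. Section 5.8 ("Participants will be removed from study when any of the following criteria apply") lists only loss to follow-up, withdrawal of consent for data submission, and death. A patient removed under 6.2 has stopped therapy, so 5.7 still applies. The document uses the word loosely elsewhere: 5.6 "submits a completed Off Treatment form to ODQ when a participant comes off study" and 5.4 "withdrawal of the patient from the study during cycle 1". The phrase in 6.2 is an editorial slip.

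It is also fair to say that the censoring rule is pre-specified and that, with the Wald test, even four early stoppers leave power at about the planned 85%. Both points stand, and they limit the weight of this one.

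**Conclusion.** The point holds as a low-cost improvement. Footnote K leaves patients who stop without progression with no planned progression data after the off-treatment visit, and the censoring rule then treats progression and death unequally. If one or four of 25 patients are due to stop in months 1-6, the cost at the 20-month alternative is about 1 point or about 4 to 5 points of power. Type I error under the 14.5-month rule changes little, so the documents do not support a claim that the primary test becomes invalid or too liberal.

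These sizes rest on assumed numbers of stoppers, exponential times, assumed post-progression survival and an unchanged hazard after stopping. If risk does change when treatment stops, censoring is informative in a way these figures do not capture. Correcting 6.2 changes no result.

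**What to change.** Amend footnote K, and 5.7 to match. For patients who stop protocol therapy without progression, collect tumour assessments done in routine care at the existing 3-4 monthly record review until progression or new anticancer therapy, in addition to survival status. No extra scans or visits are required. The cost is some added data collection, and routine-care scans may not follow the eight-week schedule, so some progression dates will be less exact.

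As an editorial correction, 6.2 should refer to removal from protocol therapy. Section 5.8 needs no change.

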6.3 Dose Modifications

The first dose reduction for any toxicity must include a reduction in LY3022855. Further dose reductions will be based on the offending medication(s) according to the schedule outlined in **Table 22**. In the event the treating investigator feels all three medications are responsible for the toxicity, all medications can be reduced. Dose reductions below 25 mg once per week of LY3022855 will not be permitted. Reductions below 480 mg BID of vemurafenib or 20 mg daily of cobimetinib will not be permitted.

A maximum of two dose reductions will be allowed with any one of the medications. If a patient requires more than two dose reductions with any one of the study medications, they should be discontinued from protocol therapy. Exceptions are possible in the event a patient is not tolerating the vemurafenib and/or cobimetinib despite maximal dose reductions but is deriving clinical benefit. In this circumstance, a patient may be allowed to continue on protocol therapy and receive LY3022855 either alone or in combination with just the vemurafenib or cobimetinib if agreed upon with the principal investigator.

Patients undergoing dose reductions for toxicities may not be re-escalated.

Participants enrolled to the phase I portion of the trial may undergo intra-patient dose escalation if subsequent higher dose levels are proven safe as per the guidelines in **5.1** and **5.4**. Participants may only undergo dose escalations to a dose level where ≤ 1 DLT have been observed among 6 patients, two dose levels below a dose level where ≤ 1 out of 3 patients have experienced DLTs, or the dose level that has been declared the RP2D. Under no circumstances may a patient escalate to a dose level above the MTD. Patients must have been on study for at least two cycles with no DLTs or DLT-equivalent toxicity to be eligible for dose escalation.

Table 22: Dose Modifications

Original Dose Level	LY3022855 Reduction	Vemurafenib Reduction*	Cobimetinib Reduction*		
1	1 st Reduction: 25 mg weekly	1 st Reduction: 720 mg BID	1 st Reduction: 40 mg once daily		
	2 nd Reduction: Discontinue protocol therapy	2 nd Reduction: 480 mg BID	2 nd Reduction: 20 mg once daily		
2	1st Reduction: 50 mg weekly	2 nd Reduction: 720 mg BID	1 st Reduction: 40 mg once daily		
	2 nd Reduction: 25 mg weekly	2 nd Reduction: 480 mg BID	2 nd Reduction: 20 mg once daily		
3	1 st Reduction: 75 mg weekly	1 st Reduction: 720 mg BID	1 st Reduction: 40 mg once daily		
	2 nd Reduction: 50 mg weekly	2 nd Reduction: 480 mg BID	2 nd Reduction: 20 mg once daily		

^{*:} Vemurafenib and cobimetinib may be reduced as per the FDA prescribing information

6.4 Overdose management

There are no known antidotes for over-dosage of LY3022855, vemurafenib, or cobimetinib. In the case of suspected overdose, monitor hematologic parameters, serum chemistry, vital signs, cardiac function, and provide supportive care as necessary.

7. ADVERSE EVENTS: LIST AND REPORTING REQUIREMENTS

Adverse event (AE) monitoring and reporting is a routine part of every clinical trial. The following list of reported and/or potential AEs (7.1) and the characteristics of an observed AE (7.2 and 7.3) will determine whether the event requires expedited reporting in addition to routine reporting.

7.1 Expected Toxicities

Please refer to the FDA prescribing information for vemurafenib and cobimetinib, along with the IB for LY3022855 for the most comprehensive information regarding expected toxicities associated with treatment.

Reasonably anticipated serious adverse events for patients with advanced melanoma who receive LY3022855 include:

- Fatigue
- Nausea/vomiting/anorexia
- Diarrhea
- Elevation of hepatic transaminases
- Increases in LDH
- Increases in blood creatine phosphokinase
- Lymphopenia

Fatigue has been the most frequent toxicity reported following treatment with LY3022855, followed by elevation in hepatic transaminases and increases in blood creatine phosphokinase (CPK). Increased creatinine has been the most frequently reported AE for patients treated with the combination of vemurafenib and cobimetinib, followed by increased CPK, and liver transaminase increases.

Reasonably anticipated overlapping toxicities for the combination may include hepatotoxicity, CK elevations, and cardiomyopathy.

7.2 Adverse Event Characteristics

• CTCAE term (AE description) and grade: The descriptions and grading scales found in the revised NCI Common Terminology Criteria for Adverse Events (CTCAE) version 4.03 will be utilized for AE reporting. All appropriate treatment areas should have access to a copy of the CTCAE version 4.03. A copy of the CTCAE version 4.03 can be downloaded from the CTEP web site:

http://ctep.cancer.gov/protocolDevelopment/electronic applications/ctc.htm.

• For expedited reporting purposes only:

- AEs for the agent(s) that are listed above should be reported only if the adverse event varies in nature, intensity or frequency from the expected toxicity information which is provided.

• **Attribution** of the AE:

- Definite The AE *is clearly related* to the study treatment.
- Probable The AE *is likely related* to the study treatment.
- Possible The AE *may be related* to the study treatment.
- Unlikely The AE *is doubtfully related* to the study treatment.
- Unrelated The AE *is clearly NOT related* to the study treatment.

7.3 Serious Adverse Events

A serious adverse event (SAE) is any adverse event during this study that results in one of the following outcomes:

- Death
- Hospitalization for greater than 24 hours
- Prolonging an existing inpatient hospitalization
- A life-threatening experience (that is, immediate risk of dying)
- Persistent or significant disability/incapacity
- Congenital anomaly/birth defect
- Considered significant by the investigator for any other reason

Previously planned (prior to signing the informed consent form) surgeries, and non-disease related elective surgeries planned during the course of the study, should not be reported as SAEs unless the underlying medical condition has worsened or appeared during the course of the study.

Preplanned hospitalizations or procedures for preexisting conditions that are already recorded in the patient's medical history at the time of study enrollment should not be considered SAEs. Hospitalization or prolongation of hospitalization without a precipitating clinical AE (e.g., for the administration of study therapy or other protocol-required procedure) should not be considered SAEs.

Important medical events that may not result in death, be life-threatening, or require hospitalization may be considered SAEs when, based on appropriate medical judgment, they may jeopardize the patient and may require medical or surgical intervention to prevent one of the outcomes listed in this definition.

Death due to disease progression should not be reported as an SAE unless the investigator deems it to be related to the use of study drug.

Study site personnel must alert Eli Lilly of any SAE as soon as possible and no later than 24 hours of the investigator and/or institution receiving notification of the SAE experienced by a

patient participating in the study. The SAE reports are to be sent to Eli Lilly via fax at [name].

